10. SAFETY AND PHARMACOVIGILANCE

10.1 DEFINITION OF AN ADVERSE EVENT

An AE is defined as any untoward medical occurrence in a clinical trial patient administered a medicinal product and which does not necessarily have a causal relationship with the treatment.

An AE can therefore be any unfavorable and unintended sign (including an abnormal laboratory finding), symptom, or disease temporally associated with the use of an investigational medicinal product, whether or not considered related to the investigational medicinal product.

A new medical condition or the worsening of a pre-existing condition will be considered an AE. Stable chronic medical conditions such as arthritis that are present prior to study entry and do not worsen during the study will not be considered AEs. Worsening of the disease under study should only be recorded as an AE if the outcome is more serious than would normally be expected from the normal course of the disease in a particular patient.

In the study, any event occurring after the clinical trial subject has signed the study Informed Consent (ICF) should be recorded and reported as an AE. Those events occurring prior to drug administration will be considered to be “Non-Treatment-Emergent” AEs and those occurring after drug administration as “Treatment-Emergent” AEs.

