10.2 INTENSITY OF ADVERSE EVENTS

The intensity or severity of the AE will be characterized as:

- Mild: AE which is easily tolerated
- Moderate: AE sufficiently discomforting to interfere with daily activity
- Severe: AE which prevents normal daily activities

The maximum severity for the event should be listed when the intensity changes during the course of an AE. If the change in severity represents distinct events rather than a single event, this should be recorded as separate AEs.

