10.4 RECORDING OF ADVERSE EVENTS

Adverse Events are illnesses or signs/symptoms that appear or worsen during the testing of a drug whether or not considered related to the investigational product (synonyms = medicinal or pharmaceutical product, study drug, clinical trial materials, etc.), including side effects, injury, toxicity, or hypersensitivity reactions.

All adverse events, including observed, elicited, or volunteered problems, complaints or symptoms, are to be recorded on the Adverse Events page in the subject’s Case Report Form.

The need to capture this information is not dependent upon whether adverse events are associated with use of the investigational product.

Adverse events resulting from concurrent illnesses, reactions to concurrent illnesses, reactions to concurrent medications progression of disease states should also be recorded. In order to avoid vague, ambiguous or colloquial expressions, adverse events should be recorded in standard medical terminology rather than the subject’s own words. Signs and symptoms should be reported individually unless, in the judgment of the investigator, they can be grouped under an inclusive term (e.g., gastroenteritis in lieu of abdominal pain, nausea, vomiting, and diarrhea).

Each adverse event is to be evaluated for date/time of onset, duration, intensity, and causal relationship with the investigational product or other factors.

At every study visit, the investigator must document new AEs and the outcome of ongoing AEs. Any subject with an AE (including SAEs) or any clinically significant abnormal laboratory result or physical finding reported as an AE will be followed by the investigator until the AE resolves, resolves with sequelae, is otherwise explained by a medical condition, follow-up is not possible (document), or the subject dies.

10.4.1 Clinical Laboratory Abnormalities and Other Abnormal Assessments as AE:

Clinically significant abnormal laboratory findings or clinically significant abnormal findings from other assessments that are detected during the study or are present at baseline and significantly worsen following the start of the study will be reported as AEs. Abnormal laboratory findings or other assessments deemed as abnormal will not be reported as AEs if they are determined to be clinically insignificant.

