11.5.2 Safety Analyses

Safety evaluations will be based on the incidence, intensity, and type of AEs. Safety variables will be tabulated and presented for all patients in the Safety population.

Summarization will focus on incidence of SAEs; treatment-emergent AEs by System Organ Class (SOC) and Preferred term; AEs that are considered study-drug related; and AEs leading to study discontinuation.

Adverse events will be coded using the Medical Dictionary for Regulatory Activities (MedDRA) for purposes of summarization.

A Treatment-emergent AE is defined as any AE that occurs after administration of the study drug and through the final visit, any event that is considered study drug-related regardless of the start date of the event, or any event that is present at baseline but worsens in intensity or is subsequently considered study drug-related by the Investigator.

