### **2.6.1 Adverse Events**

AEs that occur through the TOC Visit will be summarized by System Organ Class (SOC), Preferred Term, intensity, and treatment group for treatment-emergent AEs. Summaries will also be provided for study drug-related AEs, serious AEs, and AEs leading to study discontinuation. Each patient will be counted only once for each of the incidence rates, regardless of the number of occurrences (events) the patient experiences.

A Treatment-emergent AE is defined as any AE that occurs after administration of the study drug and through the final visit, or any event that is considered study drug-related regardless of the start date of the event.

	SEC-WH-301 Statistical Analysis Plan	Revision No.: 2.0
	Document Date: 20-Mar-2020	Page 11 of 12

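### SAP 2.6.1 omits, without disclosure, the protocol's rule that a baseline event worsening in intensity is treatment-emergent; few or no events are likely to be affected

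*SAP*

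**What the plan says.** Protocol 11.5.2 defines a treatment-emergent adverse event (TEAE) by three limbs: it occurs after study drug and up to the final visit; it is judged drug-related, whenever it began; or it is "any event that is present at baseline but worsens in intensity" or is later judged related.

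SAP 2.6.1 gives the first two limbs in nearly the same form and stops at "or any event that is considered study drug-related regardless of the start date of the event". SAP 4 lists two changes from the protocol, the handling of data after the test-of-cure (TOC) visit and the basis of the symptom strata. The document history does not mention the TEAE definition either. Protocol section 11 says that changes to the analyses will be described in the SAP.

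The protocol's recording rules also bear on the point:

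- Section 10.1: "A new medical condition or the worsening of a pre-existing condition will be considered an AE". Adverse events are collected from signature of the consent form. Of pre-dose events it says "Those events occurring prior to drug administration will be considered to be" non-treatment-emergent, without the exceptions made in 11.5.2.
- Section 10.2: "The maximum severity for the event should be listed when the intensity changes during the course of an AE", but "If the change in severity represents distinct events rather than a single event, this should be recorded as separate AEs".
- Section 10.4: "Adverse Events are illnesses or signs/symptoms that appear or worsen during the testing of a drug", and "Each adverse event is to be evaluated for date/time of onset, duration, intensity, and causal relationship with the investigational product or other factors".

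**The concern.** TEAEs are a named safety endpoint (protocol 4.3.3), and SAP 2.6.1 tabulates them by system organ class, preferred term and intensity. The two documents define that endpoint differently, and a reader cannot tell whether the difference is deliberate. A programmer working from the SAP with onset dates would leave out an event that began mild before dosing and became severe after it, if it was kept as one record and judged unrelated. The protocol would count that event. If the choice is first noticed after unblinding, the event has to be classified with treatment known.

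**Working it through.** No figure in the plan depends on this point, so the check compares the texts.

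**Step 1. The limbs side by side.**

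| Limb | Protocol 11.5.2 | SAP 2.6.1 |
|---|---|---|
| Occurs after dosing, through the final visit | yes | yes |
| Drug-related, whatever the start date | yes | yes |
| Present at baseline, later judged related | yes | covered by the limb above |
| Present at baseline, worsens in intensity | yes | absent |

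**Step 2. Where the definitions differ.** Let O = onset after dosing, R = judged related, W = worsens after dosing (1 = yes, 0 = no). If the first limb is read by onset date:

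- Protocol: O or R or W
- SAP: O or R

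| O | R | W | Protocol | SAP |
|---|---|---|---|---|
| 0 | 0 | 0 | no | no |
| 0 | 0 | 1 | **yes** | **no** |
| 0 | 1 | 0 | yes | yes |
| 0 | 1 | 1 | yes | yes |
| 1 | 0 | 0 | yes | yes |
| 1 | 0 | 1 | yes | yes |
| 1 | 1 | 0 | yes | yes |
| 1 | 1 | 1 | yes | yes |

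They differ in 1 of 8 combinations: pre-dose onset, unrelated, worsens after dosing. If post-dose worsening is instead taken to be an event that itself occurs after dosing, the SAP becomes (O or W) or R, which equals the protocol rule, and they differ in 0 of 8. The table shows what the onset reading implies; it does not establish that reading.

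**Step 3. Which reading the text favours.** Two points favour onset date. The SAP's second limb sets the start date aside for related events, which is needed only if the first limb works by start date. Protocol 11.5.2 has the same first limb and still adds worsening separately, which would be redundant if the first limb already covered it. On the other side, 10.1 and 10.4 treat worsening as an adverse event in itself.

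**Step 4. Which events reach the differing row.** A medical-history condition that worsens after dosing is a new adverse event under 10.1. A clinically significant baseline finding is recorded as medical history, and its significant worsening is reported as an adverse event under 10.4.1. A change in severity that is a distinct event gets its own record under 10.2. All of these start after dosing and count under the SAP. What remains must meet every one of these conditions: onset after consent and before first dose, ongoing at dosing, worsening afterwards, one record at maximum severity, and judged unrelated.

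**Step 5. The window.** Table 1 and protocol 9.3.1 place consent, randomization and first dose at Visit 1 (Day 1), so the window is normally part of one visit. The lower bound is 0 of about 144 randomized patients (assuming all are dosed). The documents give no basis for an upper bound.

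**Step 6. What else would show the event.** SAP 2.6.1 does not expressly restrict the summaries of serious events and of events leading to discontinuation to TEAEs, and SAP 2.1 puts all data in listings. Only a non-serious event that did not lead to discontinuation could be missing from every summary table.

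**The case against.** The strongest reply is that the protocol's recording rules already do the work of the missing limb, and that the remainder needs a chain of conditions unlikely to be met within one visit. The first part is largely right: 10.1, 10.4 and 10.4.1 turn most worsening into new post-dose events. The second part is also right about size. Neither removes the discrepancy, because a single record with pre-dose onset is still treated differently by the two definitions under the reading that the SAP's own words favour.

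A further reply is that the protocol is not consistent with itself: 10.1 classifies by timing alone, so the SAP departs from 11.5.2 but sits close to 10.1. That stands. The SAP may also change the analysis, and it does state its definition openly. What is missing is the entry in SAP 4.

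Three stronger readings are tempting, and the documents do not support them:

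- A reader might infer that worsening of baseline conditions in general is lost from the safety tables. It is not, for the reasons in Step 4.
- A reader might infer that re-evaluation or re-screening under protocol 6.3 opens a long window between consent and dosing. That route is weak. Re-screening follows resolution of the condition, so the condition is not ongoing at first dose. The documents also do not say that the original consent carries over.
- A reader might infer that sites need a new rule requiring a separate record for every worsening. That would depart from 10.2, which keeps one record unless the events are distinct, and it would need an approved amendment under 12.2.

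**Conclusion.** The point holds and is minor. SAP 2.6.1 narrows a protocol-defined safety endpoint, and SAP 4 does not say so. The effect rests on reading the first limb by onset date, which the wording favours but does not settle. On that reading, the only events excluded are those described in Step 4. The expected number is very small or zero, and no percentage-point effect on any TEAE rate can be derived. The primary efficacy analysis and the listings do not change. The case for acting is that the definition should be settled while the data are still blinded.

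**What to change.** 1. **SAP 2.6.1:** restore the missing limb, so that an event already present at baseline counts as treatment-emergent if its intensity increases after study drug is given. If the removal was deliberate, list it in SAP 4 with a reason instead.
2. **Before unblinding:** identify any adverse event with pre-dose onset that was still ongoing at first dose, and resolve by routine data query whether it worsened after dosing. This is needed because a single record under protocol 10.2 holds the maximum severity but not when it was reached, so the restored sentence cannot be programmed from that record alone.
3. **Protocol 10.1 and 11.5.2:** reconcile the two definitions only if the protocol is being amended for another reason. Section 12.2 requires sponsor and ethics approval for any protocol change, which this point alone does not justify.

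The cost is one SAP sentence (or one SAP 4 entry) and a query that is expected to reach few or no records. Items 1 and 2 need no protocol amendment and no change to adverse event recording.

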## 2.6.2 Vital Signs

Actual values and changes from baseline to the TOC Visit will be summarized by treatment group for each vital sign assessment.

## 2.7 Interim Analyses

No interim analyses are planned.

# 3. DATA HANDLING

## 3.1 Baseline and Study Visits

Visits for all analyses will be as recorded on the Case Report Form (CRF). Baseline is defined as the last assessment (including unscheduled assessments) prior to dosing. The day of dosing is considered Day 1. Assessments will be considered Baseline if the assessment is before the date of dosing, or if the assessment was done on Day 1 and, according to the Study Schedule of Assessments, was supposed to be performed on Day 1 prior to treatment.

## 3.2 Missing Data

Patients in the mITT population whose status for the primary endpoint (Microbiological Cure) is unknown will be assumed to be not cured. Patients in the mITT subgroup of patients who have clinical symptoms of trichomoniasis at baseline whose status for the exploratory endpoint (Outcome Responder) is unknown will be assumed to be a non-responder. No other imputation of missing data will be performed.

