4.3 STUDY ENDPOINTS

4.3.1 Primary Efficacy Endpoints

The following primary endpoint will be evaluated at the TOC Visit (Study Day 6-12):

- Microbiological Cure at the TOC Visit (Microbiological Cure is defined as a negative *T. vaginalis* culture).

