7. TREATMENTS

7.1 TREATMENTS ADMINISTERED

Study medication [either Solosec (containing 2 grams of secnidazole) or matching placebo] will be orally administered, under direct observation, as a single dose with approximately 4 ounces of unsweetened applesauce. Upon completion of the primary phase (Visit 1 (baseline) to Visit 2 (Day 6-12)), patients will receive the opposite treatment (placebo patients will receive Solosec and vice versa).

The study medication may be taken without regard to meals. Water may be taken after the administration of study medication to aid in swallowing (See the Solosec Package Insert, Appendix A for more detailed information). Administration of each dose of study drug will be witnessed by a qualified study site staff member and documented on the source document.

All qualifying patients with *T. vaginalis* positive results at baseline will be asked to tell their sex partners (within at least 90 days) of their infection with *T. vaginalis* and to encourage them to seek appropriate treatment. Additionally, where allowed (based on legal and institutional restrictions) and at the discretion of the Investigator, all qualifying patients with *T. vaginalis* will be provided with a prescription for a medication for *T. vaginalis* (e.g., metronidazole 2g or tinidazole 2g) to deliver to their sex partner(s) (i.e., patient-delivered partner therapy).

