8. PROHIBITED AND RESTRICTED MEDICATIONS AND PROCEDURES

All prescription and non-prescription medications and therapies, including vitamins, herbal medicines, or other non-traditional medicines, taken from 30 days prior to the first study drug dose through the end of the study must be recorded in the eCRF.

The following medications and products are prohibited during study participation, as described below:

- Systemic antimicrobial therapies for the duration of the study, with the exception of oral antifungal therapy (e.g., oral fluconazole) to treat intercurrent conditions (e.g., vulvovaginal candidiasis);
- Topical antimicrobial/ antifungal / immunomodulatory therapies in the genital area (vagina, vulva and surrounding soft tissue), including treatments for external genital warts;
- Secnidazole, metronidazole or tinidazole treatment.
- Intravaginal paromomycin, intravaginal boric acid, nitazoxanide, intravaginal betadine (povidone-iodine), clotrimazole, acetic acid, furazolidone, gentian violet, nonoxynol-9, and potassium permanganate.
- Systemic corticosteroids (intranasal and inhaled steroids are permitted).

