11.3 POPULATIONS FOR ANALYSIS

Study Populations:

Intent-to-Treat (ITT): The ITT population will include all randomized patients.

Modified Intent-To-Treat (mITT): The mITT population will include all randomized patients who were culture positive for *Trichomonas vaginalis* and negative for other sexually transmitted infections. The primary efficacy analysis will be conducted in the mITT population.

Per-Protocol (PP): The PP population will be composed of patients in the mITT population with consideration of the following criteria: received the study medication as randomized, met inclusion and exclusion criteria, had a TOC visit between Days 6-12, and had no major protocol violations. The composition of the PP population will be finalized and documented in a review of the data conducted prior to unblinding the study database. The PP population will be used for supportive efficacy analyses.

Safety: The Safety population will be composed of all randomized patients who received any amount of study medication. All safety summaries will be based on the Safety population.

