11.6.4 Missing Data

Subjects in the mITT population whose status for the primary endpoint is unknown will be assumed to be not cured. Apart from this, no imputation of missing data will be performed.

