## 2.3 Study Populations

**Intent-to-Treat (ITT):** The ITT population will include all randomized patients. Patients will be summarized based on the randomized treatment group.

**Modified Intent-To-Treat (mITT):** The mITT population will include all randomized patients who were culture positive for *T. vaginalis* and negative for STIs (lab results will not be known until after randomization). Patients will be summarized based on the randomized treatment group.

**Per-Protocol (PP):** The PP population will be composed of patients in the mITT population with consideration of the following criteria: received the study medication as randomized, met inclusion and exclusion criteria, had a TOC visit between Days 6-12, and had no major protocol violations. The composition of the PP population will be finalized and documented in a review of the data conducted prior to unblinding the study database.

**Safety:** The Safety population will be composed of all randomized patients who received any amount of study medication. Patients will be summarized based on the treatment group actually received.

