## 3.3 Incomplete Medication Dates

If a medication has an incomplete start or stop date, the following rules will be used to determine if the medication is prior or concomitant:

- If the stop year and month are both present, the stop date will be assumed to be the minimum of the last day of the given month for the given year and the patient's final study date.
- If the stop year is present and the stop month is missing, the stop date will be assumed to be the minimum of the last day of the given year and the patient's final study date.
- Otherwise, if the stop year is missing, the stop date will be assumed to be the patient's final study date.

	SEC-WH-301 Statistical Analysis Plan	Revision No.: 2.0
	Document Date: 20-Mar-2020	Page 12 of 12

- An incomplete start date will be assumed to be the minimum of the date of study drug administration and the associated medication stop date.

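### Does the mITT primary analysis need a rule for patients who took another active drug before a negative test-of-cure culture?

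*SAP*

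**What the plan says.** Protocol 4.3.1 gives the endpoint as "Microbiological Cure at the TOC Visit (Microbiological Cure is defined as a negative" *T. vaginalis* culture). SAP 2.5.1 repeats this as a negative InPouch TV test at the TOC visit on Day 6-12. Neither text refers to other treatment. SAP 2.3 defines the mITT by culture and STI results, so medication taken after randomisation does not affect membership.

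Both documents have one default to failure. Protocol 11.6.4 reads "Subjects in the mITT population whose status for the primary endpoint is unknown will be assumed to be not cured". SAP 3.2 reads "Patients in the mITT population whose status for the primary endpoint (Microbiological Cure) is unknown will be assumed to be not cured", and extends the rule to the exploratory endpoint. A negative culture is a known status, so the default does not apply to it.

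Protocol 8 prohibits metronidazole, tinidazole and non-study secnidazole, and requires that medications "taken from 30 days prior to the first study drug dose through the end of the study must be recorded in the eCRF". Protocol 7.1 allows some patients a prescription "to deliver to their sex partner(s) (i.e., patient-delivered partner therapy"). Protocol 6.4 foresees disallowed medication and leaves withdrawal to a case-by-case decision.

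On the per-protocol (PP) set, Protocol 11.3 states "The PP population will be used for supportive efficacy analyses". SAP 2.3 admits mITT patients who, among other criteria, "had a TOC visit between Days 6-12, and had no major protocol violations", and membership is settled in a data review before unblinding. SAP 2.5 commits to running the primary and exploratory analyses in that set too.

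**The concern.** The protocol recognises that other nitroimidazoles could disturb the endpoint, yet never says in terms how a user's culture is scored in the mITT. Read literally, a negative culture after another active drug is a cure for the assigned arm. Some patients may be carrying a prescription for such a drug, meant for a partner. The only named sensitivity analysis, in SAP 2.5.1, deals with symptom strata. The PP analysis is only supportive, and the plan does not say that prohibited medication is a major violation.

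Use in the placebo arm would raise the placebo cure rate and cost power. Use in the Solosec arm would credit Solosec with another drug's effect. If the scoring really were open, it could be chosen after the results were known.

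The date rule in SAP 3.3 also looks unhelpful: "An incomplete start date will be assumed to be the minimum of the date of study drug administration and the associated medication stop date". It could move a drug started after the TOC culture to a date before it.

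**Working it through.** **Inputs.** From SAP 2.2: 50 mITT patients per arm, cure 75% on Solosec and 40% on placebo, two-sided alpha 0.05, power about 95%. From Protocol 3.3: drugs of this class cure about 90-95%; 90% is used here. The share of users, r, is not in the documents; 5%, 10% and 20% are assumed.

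**Planned power.** With p̄ the mean of the two rates and n = 50,

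power = Φ{ [|p1 − p2| − 1.96·√(2p̄(1−p̄)/n)] / √[p1(1−p1)/n + p2(1−p2)/n] }.

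For 0.75 against 0.40, p̄ = 0.575. The numerator is 0.35 − 1.96 × 0.0989 = 0.156, the denominator is 0.0925, and the power is 95.4%. This reproduces the stated figure.

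**Culture as observed.** If a share r of otherwise uncured patients takes the other drug:

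- placebo rate = 0.40 + 0.60 × 0.90 × r
- Solosec rate = 0.75 + 0.25 × 0.90 × r

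**Users scored not cured.** If a share r of all patients uses the drug regardless of outcome, the rates are 0.75(1 − r) and 0.40(1 − r).

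| r | Placebo-only use, as observed | Equal use, as observed | Equal use, users not cured |
|---|---|---|---|
| 5% | 75.0 v 42.7; power 91.9% | 76.1 v 42.7; 93.8% | 71.3 v 38.0; 92.8% |
| 10% | 75.0 v 45.4; 86.8% | 77.3 v 45.4; 91.7% | 67.5 v 36.0; 89.5% |
| 20% | 75.0 v 50.8; 71.3% | 79.5 v 50.8; 86.5% | 60.0 v 32.0; 81.2% |

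**In patients.** Placebo is expected to leave 50 × 0.60 = 30 uncured. At r = 20% that is 6 users and 6 × 0.90 = 5.4 extra cures. Solosec is expected to leave 50 × 0.25 = 12.5 uncured, giving 2.5 users and about 2 extra cures.

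**If Solosec cures 90%**, within the range in Protocol 3.3, power as observed is at least 99.5% in every case above.

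**False positives.** Take 40% in both arms, with a nominal 2.5% chance of a significant result favouring Solosec.

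- Culture as observed, use by 5%, 10% or 20% of uncured Solosec patients only: 4.6%, 7.8% or 18.9%.
- Users scored not cured, use by the same shares of placebo patients only: 4.0%, 6.1% or 12.9%.
- Equal use unrelated to arm: the two rates stay equal under either scoring, so the error rate stays at its nominal level.

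**Does the text leave the choice open?** Put the cure definition beside the mITT definition. The patient belongs to the mITT because of her culture and STI results, and she is cured because her TOC culture is negative. One classification follows, and an analyst has nothing to choose after unblinding.

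**Does SAP 3.3 matter here?** Its stated purpose is to sort medications as prior or concomitant, and no efficacy analysis uses it. The problem would arise only if a new efficacy flag were built on it. Even then, misdating could change only TOC-negative patients. They have no Visit 3 and are discharged after a telephone call (Protocol 9.3.2), so a drug started after TOC has little chance of being recorded.

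**The case for a change.** The strongest case for acting is that the protocol foresees the event, medications are already recorded, and one flag and one repeat of the Cochran-Mantel-Haenszel test would show whether users affect the result. If use were confined to placebo patients who would otherwise stay positive, scoring them not cured would restore 75% against 40% and the full 95.4% power. The PP analysis is no exact substitute, because it selects on post-randomisation events and does not name prohibited drugs as a reason for exclusion. All of this stands as an argument that an extra supportive analysis would be reasonable.

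It does not show that the plan is unsound. Use driven by persisting infection should be commoner on placebo, and as-observed scoring then works against Solosec. The 18.9% false-positive figure needs use on Solosec alone while the drug has no effect, in a double-blind trial (Protocol 7.5); the documents offer no mechanism for that. Little prompts use in either arm. The window is 6-12 days, the TOC culture result is not available at the visit, no wet mount is scheduled at Visit 2, and everyone then receives the opposite treatment.

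Nor is the alternative scoring a safe reference: it has its own one-sided error (12.9% at 20% placebo-only use) and costs more power when use is equal. Requiring the conclusion to hold under both would add a second success criterion to a plan with a single primary analysis (Protocol 11.6.1). Joint power could then not exceed 81% with equal 20% use.

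**Conclusion.** No change follows. The plan scores these patients by the culture observed, which is coherent and matches the protocol's definition of cure. The alternative is a trade-off rather than a correction.

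The likely effect is some loss of power: about 3 points at 5% placebo-only use (95.4% to 91.9%) and about 24 points at 20% (to 71.3%), the second being an extreme case. With equal use the loss is about 2 to 9 points. These figures rest on assumed rates of use and a 90% effective drug. They fade if Solosec performs as Protocol 3.3 expects of the class. The sample size and the stated power are unaffected.

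The remaining detail is one that analysts handle in ordinary reporting. SAP 2.4 already summarises concomitant medications by treatment group in the safety population, SAP 2.1 lists all data, and the PP review before unblinding is the natural place to judge prohibited-drug users. A reader of the results could see how many there were and in which arm.
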